8.4.1 Laboratory evaluations

If participants cannot visit the site for safety lab assessments conducted through central labs, local lab collection may be used during a Public Health emergency as declared by Local or Regional authorities i.e. pandemic, epidemic or natural disaster, that limits or prevents on-site study visits.

Clinically notable laboratory findings are defined in Appendix 1.

Clinically significant abnormalities must be recorded as either medical history/current medical conditions or AEs as appropriate.

Table 8-2 List of laboratory parameters

Test Category	Test Name
Hematology	Hematocrit, Hemoglobin, Platelets, Erythrocytes, Leukocytes, Erythrocyte Cell Morphology, Differential (Basophils, Eosinophils, Lymphocytes, Monocytes, Neutrophils, Bands, Other)
Chemistry	Albumin, ALP, ALT, AST, Gamma-glutamyl-transferase (GGT), Lactate dehydrogenase (LDH), Calcium, Magnesium, Phosphate, Chloride, Sodium, Potassium, Creatinine, Creatine kinase, Direct Bilirubin, Indirect Bilirubin, Total Bilirubin, Total Cholesterol, LDL Cholesterol, HDL Cholesterol, Total Protein, Triglycerides, Urea Nitrogen or Urea, Uric Acid, Amylase, Lipase, Glucose (fasting), ferritin, fibrinogen, CRP, ESR, Prothrombin Time/International Normalized Ratio (PT/INR), Glutamate dehydrogenase (GLDH) Ferritin and fibrinogen will be also measured in cases of suspicion of MAS by the investigator. Regarding CRP also see Section 8.3.1.5 . ESR will be measured at local laboratory. PT/INR and GLDH will be measured in case of liver event (See Section 10.2.1)
Urinalysis	Microscopic Panel (Erythrocytes, Leukocytes and Casts) Macroscopic Panel (Dipstick) (Bilirubin, Occult Blood, Glucose, Ketones, Leukocytes esterase, pH, Protein, Specific Gravity) In case blood and/or leukocytes, and/or protein show traces/values in the 'dipstick' evaluation at the site, a macroscopic and microscopic examination including RBC, WBC, and casts will be performed at the central lab.
Hepatitis markers	Hepatitis B Virus DNA, Hepatitis B Virus Surface Antigen, Hepatitis B Virus Surface Antibody, Hepatitis B Virus Core Antibody, anti-HCV (baseline)
Additional test	HIV test
Pregnancy Test	Serum / Urine pregnancy test (refer to 'Pregnancy and assessments of fertility' Section 8.4.3)

8.4.2 Electrocardiogram (ECG)

Electrocardiograms (ECGs) must be recorded after 10 minutes rest in the supine position to ensure a stable baseline. The preferred sequence of cardiovascular data collection during study visits is ECG collection first, followed by vital signs, and blood sampling. The QT interval corrected by Fridericia's formula (QTcF) should be used for clinical decisions.

Single 12-lead ECGs are collected. The original ECGs on non-heat-sensitive paper or a certified copy on non-heat sensitive paper, appropriately signed, must be collected and archived at the study site.

For any ECGs with participant safety concerns, two additional ECGs must be performed to confirm the safety finding. A monitoring or review process should be in place for clinically significant ECG findings throughout the study and especially at baseline before administration of study treatment.

Any identifier details must be redacted, e.g., participant initials, date of birth.

Clinically significant abnormalities must be recorded on the CRF as either medical history/current medical conditions or AEs as appropriate.

8.4.3 Pregnancy and assessments of fertility

All pre-menopausal women who are not surgically sterile will have pregnancy testing. Additional pregnancy testing might be performed if requested by local requirements.

Female participants of child-bearing potential must be informed of the need to prevent pregnancy during the study. Please refer to [Section 5.2](#) for effective contraception methods. A

serum pregnancy test is required at Screening. Urine pregnancy tests will be performed as indicated in [Table 8-1](#).

If participants cannot visit the site to have serum pregnancy tests during a Public Health emergency as declared by Local or Regional authorities i.e. pandemic, epidemic or natural disaster, that limits or prevents on-site study visits, urine pregnancy test kits may be used. Relevant participants can perform the urine pregnancy test at home and report the result to the site. It is important that participants are instructed to perform the urine pregnancy test first and only if the test result is negative proceed with the administration of the study treatment. A communication process should be established with the participant so that the Site is informed and can verify the pregnancy test results (e.g., following country specific measures).

Assessments of fertility

Medical documentation of oophorectomy, hysterectomy, or tubal ligation must be retained as source documents. Subsequent hormone level assessment to confirm the woman is not of child-bearing potential must also be available as source documentation in the following cases:

1. Surgical bilateral oophorectomy without a hysterectomy
2. Reported 12 months of natural (spontaneous) amenorrhea with an appropriate clinical profile.

In the absence of the above medical documentation, Follicle Stimulating Hormone (FSH) testing is required of any female participant regardless of reported reproductive/menopausal status at screening/baseline.

8.4.4 Other safety evaluations

Local tolerability

Local tolerability at the site of subcutaneous injection will be evaluated by a physician at each administration visit starting from Day 1 after study drug administration and, in case of any local reaction, at each clinical visit until it has disappeared.

Macrophage Activation Syndrome (MAS)

Occurrence of biologic features of MAS such as hemorrhages, central nervous system dysfunction, hepatomegaly, serum fibrinogen level < 2.5 g/L, cytopenia, hypertriglyceridemia, decreased platelet count, increased aspartate transaminase, hyperferritinemia ([Ravelli et al 2005](#)) must be carefully monitored by the investigator. Significant findings which meet the definition must be recorded in the Adverse Event eCRF for subsequent adjudication by the MAS Adjudication Committee.

8.4.5 Appropriateness of safety measurements

The safety assessments selected are standard for this indication/participant population.

8.5 Additional assessments

8.5.1 Clinical Outcome Assessments (COAs)

CCI

Trial Feedback

Trials have an option of including an anonymized questionnaire, 'Trial Feedback Questionnaire' for participants to provide feedback on their clinical trial experience. Individual participant level responses will not be reviewed by investigators. Responses would be used by the sponsor (Novartis) to understand where improvements can be made in the clinical trial process. This questionnaire does not collect data about the participant's disease, symptoms, treatment effect or AEs and therefore would not be trial data. Should any spontaneous information be collected about AEs, this would be transferred to the safety database.

8.5.2 Pharmacokinetics (PK), immunogenicity (IG) and pharmacodynamic (PD) assessments

PK, IG and PD samples will be collected at the visits defined in the assessment schedule (Table 8-1). Follow instructions outlined in the laboratory manual regarding sample collection, numbering, processing and shipment. See the potential use of residual samples for more information.

The number of samples/blood draws and total blood volume collected will not exceed those stated in the protocol.

PK samples will be obtained pre-dose of ACZ885 and evaluated in all participants at all dose levels. Whole blood samples will be collected and serum samples will be analyzed to characterize the disposition of ACZ885. The detailed method description to assess canakinumab concentration will be described in the bioanalytical raw data of the study and in the respective Bioanalytical Data Report (BDR).

The anti-drug antibodies (ADAs) against canakinumab will be assessed in serum using a validated immunoassay assay. Details of the method will be provided in the BDR.

Total IL-1 β (sum of IL-1 β free and bound to canakinumab) will be assessed. Details of the analytical methods to assess total IL-1 β in serum will be described in the BDR.

The image shows a large, bold, red logo consisting of the letters 'C', 'C', and 'I' in a stylized, sans-serif font. The logo is positioned on the left side of a dark, solid-colored rectangular area that occupies the bottom third of the page. The 'C's are slightly open at the top, and the 'I' is a simple vertical bar.

9 Discontinuation and completion

9.1 Discontinuation from study treatment and from study

9.1.1 Discontinuation from study treatment

Discontinuation of study treatment for a participant occurs when study treatment is permanently stopped for any reason (prior to the planned completion of study treatment administration, if any) and can be initiated by either the participant or the investigator.

The investigator must discontinue study treatment for a given participant if, he/she believes that continuation would negatively impact the participant's well-being.

Discontinuation from study treatment is required under the following circumstances:

- Participant/guardian decision
- Pregnancy
- Use of prohibited treatment as per recommendations in the prohibited treatment section
- Any situation in which continued study participation might result in a safety risk to the participant
- Any severe or serious adverse event that is not compatible with administration of study medication, including adverse events that require treatment with an unacceptable co-medication
- Onset of malignancy
- Occurrence of uncontrolled life-threatening infection
- Any other protocol deviation that results in a significant risk to the participant's safety

The investigator should consider discontinuing participants from study treatment who experience a clinically important worsening of disease activity compared to baseline at two consecutive visits after Week 4. A clinically important worsening will be defined as participants who do not meet the adapted ACR30 criteria by Week 12 or participants with non-response (defined as Adapted ACR <30) at two consecutive visits at any time in the study beginning at Week 12.

All participants who discontinue will complete an EOS visit, be discontinued from the trial and be treated as per standard local medical practice (see also [Section 10.1.3](#) for information on SAE reporting following the last dose of study medication).

If discontinuation from study treatment occurs, the investigator should make a reasonable effort to understand the primary reason for the participant's discontinuation from study treatment and record this information.

Participants who discontinue from study treatment agree to return for the end of treatment and follow-up visits indicated in the Assessment Schedule (refer to Section 8).

If the participant cannot or is unwilling to attend any visit(s), the site staff should maintain regular telephone contact with the participant, or with a person pre-designated by the participant. This telephone contact should preferably be done according to the study visit schedule.

After discontinuation from study treatment, at a minimum, in abbreviated visits, the following data should be collected at clinic visits or via telephone/email contact:

- New / concomitant treatments
- Adverse Events / Serious Adverse Events

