Discontinuation from study	Point/time when the participant permanently stops receiving the study treatment and further protocol required assessments or follow-up, for any reason. No specific request is made to stop the use of their samples or data.
Discontinuation from study treatment	Point/time when the participant permanently stops receiving the study treatment for any reason (prior to the planned completion of study intervention administration, if any). Participant agrees to the other protocol required assessments including follow-up. No specific request is made to stop the use of their samples or data.
Dosage	Dose of the study treatment given to the participant in a time unit (e.g. 100 mg once a day, 75 mg twice a day)
Electronic Data Capture (EDC)	Electronic data capture (EDC) is the electronic acquisition of clinical study data using data collection systems, such as Web-based applications, interactive voice response systems and clinical laboratory interfaces. EDC includes the use of Electronic Case Report Forms (eCRFs) which are used to capture data transcribed from source data/documents used at the point of care
Enrollment	Point/time of participant entry into the study at which informed consent must be obtained. The action of enrolling one or more participants
Estimand	As defined in the ICH E9(R1) addendum, estimand is a precise description of the treatment effect reflecting the clinical question posed by the trial objective. It summarizes at a population-level what the outcomes would be in the same participants under different treatment conditions being compared. Attributes of an estimand include the population, variable (or endpoint) and treatment of interest, as well as the specification of how the remaining intercurrent events are addressed and a population-level summary for the variable.
Intercurrent events	Events occurring after treatment initiation that affect either the interpretation or the existence of the measurements associated with the clinical question of interest.
Investigational drug/ treatment	The drug whose properties are being tested in the study
Medication number	A unique identifier on the label of medication kits
Off-site	Describes trial activities that are performed at remote location by an off-site healthcare professional, such as procedures performed at the participant's home.
Other treatment	Treatment that may be needed/allowed during the conduct of the study (i.e. concomitant or rescue therapy)

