2.1 Primary estimands

The primary clinical question of interest is: What is the benefit of Canakinumab in achieving clinical improvement for Japanese AOSD participants without increased use of corticosteroids regardless of study treatment discontinuations for any reason?

The justification for the primary estimand is that it will capture the actual effect of canakinumab in the condition that participants use stable dose of corticosteroids. Further details can be found in [Section 12](#).

The primary estimand is described by the following attributes:

1. Population: Japanese AOSD participants. Further details about the population are provided in [Section 5](#).
2. Endpoint: Adapted ACR 30 response at Week 8
3. Treatment of interest: canakinumab 4 mg/kg s.c (maximum of 300 mg) with stable dose of corticosteroids.

Handling of remaining intercurrent events:

1. Systemic corticosteroid dose increase and/or iv corticosteroid use before Week 8 for any reason: consider as non-response (Composite variable strategy)
2. Study treatment discontinuation for any reason: ignore (if adapted ACR 30 at Week 8 is available, it will be included in the analysis) (Treatment policy strategy)

The summary measure: Proportion of participants who achieve adapted ACR 30 at Week 8

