7.1 Pediatric Assent

In pediatric participants (< 20 years of age) parental permission and, whenever possible, pediatric assent is needed instead of the procedure for informed consent used for research involving adults. In general, one or both parents or a guardian must be provided with the information ordinarily required for informed consent, so that they may decide whether to allow the child to participate, and children capable of assent must also express their willingness to participate. These forms will be submitted for IRB/IEC approval.

8 Visit schedule and assessments

The Assessment Schedule ([Table 8-1](#)) lists all of the assessments and when they are performed. All data obtained from these assessments must be supported in the participant's source documentation.

Participants should be seen for all visits/assessments as outlined in the assessment schedule ([Table 8-1](#)) or as close to the designated day/time as possible. Missed or rescheduled visits should not lead to automatic discontinuation.

Participants who discontinue from study treatment are to return for the end of treatment visit as soon as possible, and attend the follow-up visits as indicated in the Assessment Schedule.

Participants who discontinue from study or withdraw their consent/oppose the use of their data/biological samples should be scheduled for a final evaluation visit if they agree, as soon as possible, at which time all of the assessments listed for the final visit will be performed. At this final visit, all dispensed investigational product should be reconciled, and the AE and concomitant medications not previously reported must be recorded on the CRF.

As per [Section 4.6](#), during a Public Health emergency as declared by Local or Regional authorities i.e. pandemic, epidemic or natural disaster that limits or prevents on-site study visits, alternative methods of providing continuing care may be implemented by the investigator as the situation dictates. If allowable by a local Health Authority and depending on operational capabilities, phone calls, virtual contacts (e.g. tele consult) or visits by site staff/ home nursing

staff to the participant's home, can replace on-site study visits, for the duration of the disruption until it is safe for the participant to visit the site again.

Period	Screening	Treatment																

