## **2.6.3 Handling of missing values/censoring/discontinuations**

If the successful tapering of corticosteroids can not be derived due to missing information, it will be imputed with the last available data from Week 8 to Week 28 (last observation carried forward (LOCF) approach).

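### Protocol 9.1.1 both ends trial participation and asks for return visits when treatment stops, so relabelled EOS visits, non-responder imputation and LOCF can stand in for treatment-policy data at Weeks 8 and 28

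*Protocol*

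**What the plan says.** **What happens when treatment stops.** Protocol 9.1.1 gives two instructions:
- Everyone who discontinues has an EOS visit and is then to "be discontinued from the trial and be treated as per standard local medical practice".
- "Participants who discontinue from study treatment agree to return for the end of treatment and follow-up visits indicated in the Assessment Schedule".

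Protocol Section 8 supports the second: those who stop treatment have an end-of-treatment visit as soon as possible and "attend the follow-up visits as indicated in the Assessment Schedule". So does the glossary entry for discontinuation from study treatment: "Participant agrees to the other protocol required assessments including follow-up". In Table 8-1, as far as it is legible, the only column after the treatment visits is EOS. Section 9.1.1 also sets a floor: "After discontinuation from study treatment, at a minimum, in abbreviated visits, the following data should be collected", followed by two items, new or concomitant treatments and adverse events.

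**What the estimands say.** Protocol 2.1 on the primary: "Study treatment discontinuation for any reason: ignore (if adapted ACR 30 at Week 8 is available, it will be included in the analysis"; it names this treatment policy. Protocol 2.2 applies treatment policy to stopping after Week 8 for the key secondary estimand, tapering success at Week 28.

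**What fills the gaps.**
- Primary: a missing Week 8 adapted ACR 30 is non-response, whatever the reason (Protocol 12.4.4, SAP 2.5.4).
- Both: EOS visits are mapped to analysis visits by SAP Table 2-1 (SAP 2.1.2 and 2.14).
- Key secondary: Protocol 12.5.1 provides LOCF where body weight is missing. SAP 2.6.3 provides it for missing information in general: "it will be imputed with the last available data from Week 8 to Week 28". SAP Section 4, on changes to protocol-specified analyses, reads NA.

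**The concern.** Treatment policy asks for the outcome at the scheduled time whether or not treatment continued, so it depends on collecting that outcome after stopping. Sites can follow either sentence of 9.1.1. If they follow the first, the participant leaves at EOS, close to the time of stopping, and goes to local care. The value used at Week 8 or Week 28 is then a rule's output or a measurement from around the time of stopping.

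For the primary endpoint the main substitute, non-response, is conservative. For the key secondary endpoint it is not necessarily so: a success reached while on canakinumab can be reported as a Week 28 success for someone no longer treated or observed. The study is intended to support a registration dossier, and the numbers are small enough for single participants to matter.

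**Working it through.** The plan states no figure on this point and the sample-size section is redacted, so nothing can be reproduced. The check traces the rules and then sizes their effect.

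**1. Which EOS visits become a Week 8 or Week 28 value (SAP Table 2-1)**

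| | Week 8 | Week 28 |
|---|---|---|
| Planned day | 57 | 197 |
| EOS window | 32–60 | 173–200 |
| Earliest mapped day, days before plan | 57 − 32 = 25 | 197 − 173 = 24 |
| Possible early EOS days | Days 2–56: 55 | Days 58–196: 139 |
| Of these, mapped to the target visit | Days 32–56: 25 (25/55 = 45%) | Days 173–196: 24 (24/139 = 17%) |

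The Week 28 count starts at Day 58 because the key secondary population must have been dosed at Week 8. These are counts of days, not probabilities of stopping. Day 32 is only 3 days after the planned Week 4 visit (Day 29).

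**2. What happens outside those windows, if participants exit at EOS**
- Primary: no Week 8 value, so non-response under SAP 2.5.4.
- Key secondary: SAP 2.6.1 includes discontinuers who had a Week 28 assessment and is silent on those who did not. SAP 5.6.1 assumes steroid-free status only while the participant continues the study. The outcome is then underivable and SAP 2.6.3 carries the last value forward.

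Illustration (invented case): a participant stops after the Week 16 dose, has EOS on Day 125 (window 117–144, so Week 20), and meets the tapering criteria then. LOCF reports success at Day 197, which is 197 − 125 = 72 days after last being seen.

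**3. Weight of one participant**
- 1/11 = 9.1 points (first 11 participants).
- 1/14 = 7.1 points (all 14).
- SAP 2.6.2 notes that the tapering denominator can be smaller than the FAS; with 10, for example, 1/10 = 10.0 points.

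**4. Effect on the primary test**

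z = (x/n − 0.40)/√(0.40 × 0.60/n), n = 11, one-sided 0.025, no continuity correction:
- x = 8: z = 2.216, p = 0.0134, rejects.
- x = 7: z = 1.600, p = 0.0548, does not reject.

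If a continuity correction is applied to the test, x = 8 gives p = 0.0282 and x = 9 gives p = 0.0058, so the boundary moves to 9. Either way, one leaver's classification can decide the result.

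The chance of at least 8 responders when k of the 11 are set to non-response is the binomial tail P(X ≥ 8) with 11 − k trials. The design response rate is redacted and no dropout rate is given, so both are assumptions:

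| True rate | k = 0 | k = 1 | k = 2 | k = 3 |
|---|---|---|---|---|
| 0.70 | 0.570 | 0.383 | 0.196 | 0.058 |
| 0.80 | 0.839 | 0.678 | 0.436 | 0.168 |
| 0.90 | 0.981 | 0.930 | 0.775 | 0.430 |

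The k = 0 column is also what full follow-up would give if leavers responded at the same rate as others, so it is an upper bound.

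**The case against.** A reader might infer that the treatment-policy strategy has no data at all. The documents do not support that. Table 8-1 schedules the adapted ACR assessment at EOS, and the SAP maps EOS to an analysis visit. Dosing is every 4 weeks, so someone who stops after the Week 4 dose may next be seen near Day 57 and have a genuine Week 8 value.

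The primary endpoint is also largely covered. Use of data after stopping is expressly conditional on availability, every participant has a defined Week 8 value, and the default is prespecified and conservative. That objection stands. What remains on the primary side is the follow-up contradiction and the early relabelling.

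A reader might also infer that LOCF does inflate the tapering proportion. That is not shown. Success requires a maintained adapted ACR 30 (Protocol 8.3.2), and 9.1.1 asks investigators to consider stopping for non-response at two consecutive visits from Week 12. Those leavers would normally carry a failure forward. Leavers for other reasons, such as an adverse event or their own decision, could carry a success.

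Finally, SAP 5.6.1 illustrates missing information with body weight and frequency, so SAP 2.6.3 might not be meant for absent visits. But its heading includes discontinuations and its wording sets no such limit. On the narrow reading, a leaver with no Week 28 visit would have no rule at all.

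Two cautions stand: part of Table 8-1 is illegible, and the post-stopping data list is a minimum that does not forbid collecting more.

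**Conclusion.** The point holds in limited form. The two sentences in 9.1.1 conflict. Under the exit-at-EOS reading, off-treatment outcomes at Weeks 8 and 28 are collected only when EOS falls in a mapping window, and other rules substitute under a treatment-policy label. The key secondary endpoint is the more exposed: few early EOS days map to Week 28, and the SAP has broadened LOCF beyond the protocol without declaring it.

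The size is 9.1 points per affected participant of 11, 7.1 of 14, and more on a smaller tapering denominator. A total cannot be given. A reader might apply an assumed dropout rate to all 14 participants, but the documents give no rate, those who stop before the Week 8 dose are outside the tapering population, and carried values need not be successes. Nor do the documents justify relabelling the estimands as composite: how absent data are filled is a missing-data matter, and the primary question is framed regardless of stopping treatment.

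**What to change.** 1. Reconcile the two sentences in Protocol 9.1.1 with Section 8, the glossary, Table 8-1 and the minimum data list. State whether Week 8 and Week 28 efficacy data are collected after treatment stops.
2. In SAP 2.6.3, restrict LOCF to missing body weight, as in Protocol 12.5.1. Count participants with no Week 28 assessment as tapering failures. This is a missing-data rule that matches the primary endpoint and leaves the estimand label unchanged. Record any departure from the protocol in SAP Section 4, including any rule kept for other missing dose items such as frequency.
3. Add a sensitivity analysis in which early EOS visits relabelled Week 8 or Week 28 are treated as missing, hence as non-response or tapering failure.

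The cost is wording and one extra analysis. The key secondary proportion may be slightly lower. SAP 2.14 dates the point at which the first 11 participants had reached Week 28 or discontinued to 6 December 2022, before Amendment 3 of 19 May 2023, in an open-label study. New protocol wording cannot recover their visits. The change should therefore be documented as made after those data were collected, with the result under the SAP's current LOCF rule shown alongside.
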